10.10. Appendix 10: Protocol Amendment History

The Protocol Amendment Summary of Changes Table for the current amendment is located directly before the Table of Contents (TOC).

Amendment [a]: (15 Feb 2022)

This amendment is considered to be nonsubstantial. **Overall Rationale for the Amendment**

The overall rationale for the changes implemented in the protocol amendment is to update the insulin degludec dose adjustments so that it will more closely reflect those for LY3209590.

Section # and Name	Description of Change	Brief Rationale
Section 1.1 Synopsis	Visit and Week numbers were changed and an additional row was added to the table to indicate that insulin degludec dose adjustments may occur every 4 weeks after Week 12 (Visit 15)	Table was modified to reflect the changes in insulin degludec dose adjustments
Section 1.2 Schema	Added “CGM Visits” to Safety Follow-Up section	Correction-this section was missing in original schema
Section 1.3.1 Schedule of Activities	Demographics comment-replaced “gender” with “sex”	Preferred terminology
Section 1.3.1 and 1.3.2 Schedule of Activities	Added the following text to ECG comment-“ECGs will be performed prior to collection of any blood samples”	For clarification
Section 4.3 Justification for Dose	Text was changed to indicate that insulin degludec dose adjustments should occur weekly from Visits 4 to 15 (Weeks 1 to 12) and then every 4 weeks thereafter.	The text was modified to be consistent with LY3209590 dose adjustments
Section 6.1 Study Intervention(s) Administered	Added the following text to Anatomical Location of Injections –“ Injections may be administered in the abdomen, thigh, arm, or buttock. Refer to the IFU for complete instructions on dose administration.	Anatomical location of insulin injections added to address FDA feedback to include acceptable anatomical locations for insulin administration in the protocol
Section 6.5.1.2 LY3209590 Dose Adjustment Based on FBG	Addition of the following sentence: “If the participant experienced any documented BG \leq 70 mg/dL (\leq 3.9 mmol/L) in the previous	To emphasize that, in the occurrence of a hypoglycemia event $<$ 70, insulin doses should not increase

	week, the dose should not be increased”	

4.5.3. Tertiary Safety Endpoints	26
4.6. Safety Analyses.....	26
4.6.1. Extent of Exposure.....	26
4.6.2. Adverse Events	27
4.6.3. Additional Safety Assessments.....	32
4.6.4. Device Product Complaints	41
4.7. Other Analyses.....	41
4.7.1. Immunogenicity	41
4.7.2. Subgroup analyses	42
4.8. Interim Analyses	44
4.8.1. Data Monitoring Committee (DMC)	44
4.9. Changes to Protocol-Planned Analyses	44
5. Sample Size Determination	45
6. Supporting Documentation.....	46
6.1. Appendix 1: Demographic and Baseline Characteristics	46
6.2. Appendix 2: Treatment Compliance.....	46
6.3. Appendix 3: Clinical Trial Registry Analyses	47
6.4. Appendix 4: Concomitant Medication.....	47
6.5. Appendix 5: Protocol Deviations.....	48

6.6.	Appendix 6: Derivation of CGM Variables.....	48
6.6.1.	Glucose in Target Ranges, Hypoglycemia or Hyperglycemia.....	49
6.6.2.	Hypoglycemic Episode	51
6.6.3.	Mean Glucose and Glucose Management Indicator	52
6.6.4.	Glycemic Variability.....	52
6.7.	Appendix 7: MedDRA PT for Diabetic Retinopathy or Maculopathy	54
6.8.	Appendix 8: MedDRA PT for Peripheral Edema	56
6.9.	Appendix 9: Empirical Estimation of Relative Event Rate	57
6.10.	Appendix 10: Definition for Persistent-Recurrent Hypoglycemia	58
6.11.	Appendix 11: Abnormality Level Criteria for Chemistry and Hematology Laboratory Results	59
6.12.	Appendix 12: Interaction Effect for Subgroup Analysis – Treatment Regimen Estimand	60
6.13.	Appendix 13: Statistical Analysis for China	60
6.14.	Appendix 14: Statistical Analysis for Japan	61
7.	References.....	62

Version history

This Statistical Analysis Plan (SAP) for study I8H-MC-BDCX is the 3rd version and approved prior to the final database lock. The 1st version of the SAP was approved prior to the first participant visit. The SAP versions are based on the protocol, protocol amendment (a), and protocol amendment (b) approved on 04 Feb 2022, 15 Feb 2022, and 13 May 2022, respectively.

Table 1. SAP Version History Summary

Version	Section # and Name	Description of Change	Brief Rationale
Version 2, Jan 22, 2024	1.1. Objectives, Endpoints, and Estimands	Clarify the hypoglycemia endpoint included in the tertiary composite endpoints are level 2 or 3	For clarity
	2.1. Multiplicity Adjustment	Add the details of type I error control strategy and graphic testing scheme	Add additional information for clarity
	3. Analysis Sets	For EAS2, update data cutoff for degludec arm	The change is based on PK profile
	3. Analysis Sets	CGM primary analysis population definition	For clarity
	4.1. General Considerations	Update the definitions of baseline and post-baseline observations for different analysis	For clarity and consistency with data collection
	4.3.3.and 4.4.1.3. Sensitivity Analysis	
 Update the two-way tipping point analysis in 4.3.3. Add sensitivity analyses by including inadvertently enrolled participants for primary and key secondary efficacy analyses 	To address regulatory feedback
	4.5.2. Tertiary Efficacy Endpoints	Use EAS1 for the binary outcome endpoints and update the analysis details.	To address regulatory feedback
	4.6. Safety Analyses	
 For laboratory analysis, removed shift analysis, Treatment emergent high/low and add elevated or low values meeting specified levels. Use risk difference and 95% for safety categorical data analysis. 	Per PSAP update
	4.6.3.1.2. Hypoglycemic Events Derived from CGM	Add analysis for CGM-based hypoglycemic events	Per CGM international consensus statement 2023
	4.7.1. Immunogenicity	Simplified the section and reduced analysis at the study level	Per PSAP update

Version	Section # and Name	Description of Change	Brief Rationale
	6.6. Appendix 6: Derivation of CGM Variables	Update the definition for CGM-based hypoglycemia and other updates	Per CGM international consensus statement 2023
	6.13. Appendix 13: Statistical Analysis for China and all ME2 related sections	Remove all contents related to ME2	No extended enrollment into ME2 cohort is needed for any country in order to meet the regulatory requirement.
	Throughout SAP	Minor changes and reorganization	For clarity, no change to analysis methodologies, so not detailed
Version 3, Apr 2024	4.1.General Consideration; 4.4.2.1. Other Efficacy endpoints; 2. Tertiary Efficacy Endpoints; 4.5.2. Tertiary Efficacy Endpoints	Added treatment regimen analysis for the selected secondary and tertiary endpoints (fasting serum glucose, fasting glucose from SMBG, and selected CGM parameters);	To implement FDA's feedback for BDCV's SAP
	4.4.1. Key Secondary Endpoints	Added missing data at baseline will be imputed using MI approach under MAR assumption	Addition
	4.5.2. Tertiary Efficacy Endpoints	Modified missing data handling approach for hypoglycemia in the composite endpoints of HbA1c and hypoglycemia	To implement FDA's feedback for BDCV's SAP
	4.6.3.1.1. Participant-Reported Hypoglycemic Events	Added a sensitivity analysis that considers all hypoglycemic events as one hypoglycemic event until a succeeding glucose value is ≥ 70 mg/dL	To implement FDA's feedback for BDCV's SAP
	4.6.4. Device Product Complaints	Added analysis for device product complaints	According to the new SAP template requirement
	4.7.2. Subgroup Analyses	Updated the subgroups for race	To implement FDA's feedback for BDCV's SAP
	Appendix 6. Derivation of CGM Variables	Clarified definitions of valid CGM period and session; Added sensitivity analysis for selected CGM parameters that derived from all data.	To implement FDA's feedback for BDCV's SAP

1. Introduction

The study protocol contains a summary of the planned statistical analyses of the most important endpoints, including primary and key secondary endpoints. There are no changes to the analyses described in the protocol. This SAP includes the analyses details for efficacy, safety measures, patient-reported outcomes, and parameters based on continuous glucose-monitoring (CGM). Pharmacokinetic/pharmacodynamics (PK/PD) analyses will be conducted by the PK/PD group and will be described in the PK analysis plan. The specifications for tables, figures and listings will be described in separate documents.

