5.2. Exclusion Criteria

Participants are excluded from the study if any of the following criteria applies:

Medical conditions

11. Have a diagnosis of T1D, latent autoimmune diabetes, or specific type of diabetes other than T2D, for example, monogenic diabetes, diseases of the exocrine pancreas, or drug-induced or chemical-induced diabetes.
12. Have a history of >1 episode of ketoacidosis or hyperosmolar state or coma requiring hospitalization within 6 months prior to screening.
13. Have had severe hypoglycemia episodes within 6 months prior to screening.
14. Have a history of renal transplantation, are currently receiving renal dialysis, or have an estimated glomerular filtration rate <20 mL/min/1.73 m² as calculated by the Chronic Kidney Disease-Epidemiology equation, determined by central laboratory at screening.
15. Have had a blood transfusion or severe blood loss within 90 days prior to screening.
16. Have known hemoglobinopathy, hemolytic anemia or sickle cell anemia, or any other traits of hemoglobin abnormalities known to interfere with the measurement of HbA1c.
17. Have had New York Heart Association Class IV heart failure or any of these cardiovascular conditions within 3 months prior to screening
 - acute myocardial infarction
 - cerebrovascular accident (stroke), or
 - coronary bypass surgery.

18. Have had gastric bypass (bariatric) surgery, restrictive bariatric surgery, for example Lap-Band, or sleeve gastrectomy within 1 year prior to screening.
19. Have had a significant weight gain or loss within 3 months prior to screening, for example, $\geq 5\%$.
20. Have acute or chronic hepatitis, cirrhosis, or obvious clinical signs or symptoms of any other liver disease, except non-alcoholic fatty liver disease (that is, study participants with non-alcoholic fatty liver disease are eligible for participation), and/or have elevated liver enzyme measurements, as determined by the central laboratory at screening and as indicated below:
 - a. Total bilirubin $>2x$ ULN, with the exception of previously diagnosed Gilbert's disease
 - b. ALT or serum glutamic pyruvic transaminase $>3x$ ULN
 - c. AST or serum glutamic oxaloacetic transaminase $>3x$ ULN, or
 - d. ALP $>2.5x$ ULN.
21. Have a history of an active or untreated malignancy or are in remission from a clinically significant malignancy within 5 years prior to screening.

Exceptions:

- Basal cell or squamous cell skin cancer.

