9.3.5. Safety Analyses

Safety Measures Include

- treatment exposure
- AE
- vital signs
- weight
- hypoglycemia
- laboratory measures and
- immunogenicity.

All safety analyses will be based on the SS.

Events that are newly reported after the first dose of LY3209590 or insulin degludec, or reported to worsen in severity from baseline, will be considered TEAEs. The Medical Dictionary for Regulatory Activities (MedDRA) lowest level term will be used in the treatment-emergent assessment. The maximum severity for each lowest level term during the baseline period will be used as baseline severity.

Summary statistics will be provided for incidence of

- TEAEs
- SAEs
- study discontinuation due to AEs
- intervention discontinuation due to AEs, and
- deaths.

Hypoglycemia analysis

The participant-reported hypoglycemia will be analyzed using data from the e-diary by

- Level 1 (defined by glucose value ≥ 54 to < 70 mg/dL [≥ 3.0 to < 3.9 mmol/L])
- Level 2 (defined by glucose < 54 mg/dL [< 3.0 mmol/L])
- Level 3 (severe hypoglycemia), and
- the composite of Levels 2 and 3.

The analysis periods of 0-6, 0-12, 0-26, 0-52, 12-26, and 26-52 weeks of treatment will be considered. Documented hypoglycemia will be defined as

- All documented hypoglycemia - episodes for the 24-hour period
- Non-nocturnal hypoglycemia - episodes during 6 AM to midnight, and
- Nocturnal hypoglycemia - episodes during midnight to 6 AM.

The incidence and rate of hypoglycemia will be summarized by treatment and analysis period for different types of hypoglycemia.

For continuous safety variables (for example, laboratory measures, vital signs and weight), MMRM or ANCOVA models will be used. For categorical safety variables (for example, AEs, incidence of hypoglycemia, and treatment-emergent abnormal laboratory measurements), either Fisher's exact test or logistic regression will be used for treatment comparison.

Further details for assessing all safety measures will be described in the SAP.

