Participant-reported hypoglycemia	The baseline period is the lead-in period prior to the first dose date of study treatment.	
 Treatment period starts on the first dose date of study treatment and ends 
 At Week 52 (Visit 31) if completed treatment on the last dose date of study treatment + 10 days for LY3209590, +1 day for degludec if discontinued study treatment early Post-treatment period starts from 
 Week 52 (Visit 31) +1 day if completed treatment last dose date of treatment +11 days for LY3209590, +2 days for degludec if discontinued study treatment early and ends on the last date in the study
TEAEs	The baseline period includes the screening/lead-in period up to the first dose of study treatment (The AE Start Relative to Exposure Assessment CRF is used to determine).	Safety analysis period starts after the first dose and ends at the last visit in the study including safety follow-up period.
Safety laboratory tests, vital signs, and body weight	
The baseline will be the last non-missing assessment prior to or on the first dose date of study treatment
 
Planned measurements at scheduled visits will be included.
	
 All scheduled visits after the first dose date up to Visit 802 for MMRM or ANCOVA 
Planned measurements at scheduled visits will be included.

laboratory values elevated or low, vital signs and body weight categorical measures	
Starts from the screening visit and ends prior to or on the day of first dose of study treatment .
 
All available measurements at scheduled and unscheduled visits will be included. The baseline for weight will be the last non-missing value during the baseline period.
	
Starts after the day of first dose of study treatment and ends at the last visit in the study including both treatment period and follow-up period.
 
All available measurements at scheduled and unscheduled visits in the specified analysis period will be included.

Analysis	Baseline Observations	Post-Baseline Observations
Anti-LY3209590 antibody	Refer to PSAP	Refer to PSAP
Patient-reported outcomes	The baseline will be the data collected at Visit 3	
 • All scheduled visits after Visit 3 • Last collection after Visit 3

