4.6.3.2. Laboratory and Adverse Event for Hepatic Safety

Hepatic labs include:

- alanine aminotransferase (ALT),
- aspartate aminotransferase (AST),
- total bilirubin (TBL),
- direct bilirubin (DBL),
- serum alkaline phosphatase (ALP), and

- gamma-glutamyltransferase (GGT).

When criteria are met for hepatic evaluations, investigators will conduct close monitoring of hepatic symptoms and liver tests, perform a comprehensive evaluation for alternative causes of abnormal liver tests, and complete follow-up hepatic safety CRFs.

The table below lists summary TFLs for the analysis of hepatic laboratory data.

Analysis	Details
Abnormal postbaseline categories – hepatic safety parameters	
ALT: The number and percentage of participants with a measurement greater than or equal to 1 time (1\times), 3 times (3\times), 5 times (5\times), 10 times (10\times), and 20 times (20\times) the performing laboratory ULN during the postbaseline period will be summarized for all participants with a postbaseline value.
 
AST: The number and percentage of participants with a measurement greater than or equal to 1 time (1\times), 3 times (3\times), 5 times (5\times), 10 times (10\times), and 20 times (20\times) the performing laboratory ULN during the postbaseline period will be summarized for all participants with a postbaseline value.
 
ALP: The number and percentage of participants with a measurement greater than or equal to 2 times (2\times) and 3 times (3\times) the performing laboratory ULN during the postbaseline period will be summarized for all participants with a postbaseline value.
 
TBL: The number and percentage of participants with a measurement greater than or equal to 2 times (2\times), 5 times (5\times), and 8 times (8\times) the performing laboratory ULN during the postbaseline period will be summarized for all participants with a postbaseline value.
 
DBL: The number and percentage of participants with a measurement greater than or equal to 2 times (2\times) and 5 times (5\times) the performing laboratory ULN during the postbaseline period will be summarized for all participants with a postbaseline value.
 
GGT: The number and percentage of participants with a measurement greater than or equal to 2 times (2\times) the performing laboratory ULN during the postbaseline period will be summarized for all participants with a postbaseline value.

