4.6.3.3. Clinical Laboratory Evaluations

For the following selected laboratory measures:

- Liver enzyme tests: ALT, ALP, AST, GGT, DBL and Total Bilirubin, and
- Lipid measures: Triglycerides, total cholesterol, LDL-C, and HDL-C (results from fasting samples).

MMRM model (as described in Section 4.6) will be used for the observed values, change from baseline and percentage change from baseline, for which log-transformation will be applied. Geometric LS means will be provided. Analyses will be provided in both international units (SI) and conventional units (CN) if they are different.

Box plots with descriptive statistics for the observed values and change from baseline will be provided by treatment group and visit.

For other laboratory measures, descriptive summaries will be provided for the observed values and change from baseline by treatment group and visit.

The percentages of patients with elevated or low values meeting specified levels (see Appendix 11, Section 6.11) at any time postbaseline (including scheduled and unscheduled measurements) will be summarized and compared between treatment groups using risk difference and 95% confidence interval.

A listing of abnormal laboratory analytes collected quantitatively (high or low during postbaseline using Level 2 definitions in Appendix 11, Section 6.11) and qualitatively (abnormal during postbaseline) will be provided, including participant identification, treatment group, laboratory sample collection day (that is, days from start of study drug), analyte name, abnormal result, and reference low or high limits (Level 2 cut-off value).

Scatter plots of maximum-by-maximum measurements and minimum-by-minimum measurements will not be created a-priori. They may be created if warranted after review of the planned tables and figures, using Figures 6.3 and 6.4 from the Analysis and Displays for Labs white paper (PHUSE 2022) as the model. ADaM datasets will include variables to enable the creation of scatter plots for use in either an interactive tool or for ad-hoc figures.

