4.9. Changes to Protocol-Planned Analyses

There are no changes but additional details are provided to the analyses described in the protocol.

5. Sample Size Determination

Approximately 888 participants will be randomly assigned to LY3209590 and insulin degludec in a 1:1 ratio. With the assumption of 15% dropout at Week 52, approximately 377 and 377 participants will complete 52 weeks of treatment on LY3209590 and insulin degludec, respectively.

The primary objective of this study is to test the hypothesis that LY3209590 is noninferior to insulin degludec on glycemic control as measured by change from baseline to Week 52 (Visit 31) in HbA1c in participants with T2D who are starting basal insulin for the first time. A total of 754 completers (377 on LY3209590 and 377 on insulin degludec) will provide an at least 99% statistical power to show noninferiority between LY3209590 and insulin degludec using the upper limit of a 2-sided 95% confidence interval (LY3209590 – insulin degludec) and these assumptions:

- a NIM of 0.4%,
- no true difference between treatment groups, and
- an SD of 1.1%.

This sample size also has at least 95% statistical power to show noninferiority between LY3209590 and insulin degludec using a 0.3% NIM at Week 52.

The number of participants in each subpopulation of background treatment will be approximately 50% of the study population with balanced treatment assignment to support the following secondary objectives, controlled for Type 1 error:

- To demonstrate noninferiority of LY3209590 to insulin degludec in HbA1c change from baseline to Week 52 for the subpopulation of participants using GLP-1 RAs; and
- To demonstrate noninferiority of LY3209590 to insulin degludec in HbA1c change from baseline to Week 52 for the subpopulation of participants not using GLP-1 RAs.

In each subpopulation, 188 completers for each study intervention will provide an approximately 90% statistical power to show noninferiority between LY3209590 and insulin degludec using the upper limit of a 2-sided 95% confidence interval (LY3209590 – insulin degludec) and these assumptions:

- a NIM of 0.4%,
- no true difference between treatment groups, and
- an SD of 1.1%.

The 754 completers will provide 95% statistical power to demonstrate the superiority of LY3209590 versus insulin degludec, of change in HbA1c from baseline to 52 weeks, assuming an SD of 1.1% and true mean difference is -0.3%, using the alpha of 0.05.

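### The SAP replaces treatment-emergent laboratory abnormalities with any postbaseline value meeting a mostly fixed level while stating that nothing changed, which dilutes the comparison for cut-offs common at baseline

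*SAP*

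**What the plan says.** Protocol 9.3.5 (Safety Analyses) lists examples of categorical safety variables and the tests for them: "treatment-emergent abnormal laboratory measurements), either Fisher's exact test or logistic regression will be used for treatment comparison".

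SAP 4.6.3.3 (Clinical Laboratory Evaluations) takes the percentage of participants with elevated or low values meeting the levels of Appendix 11; values "at any time postbaseline (including scheduled and unscheduled measurements) will be summarized and compared between treatment groups using risk difference and 95% confidence interval". It does not ask whether the participant met the level before dosing.

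Most Appendix 11 rows are fixed cut-offs, such as triglycerides >150 mg/dL, LDL >130 mg/dL, blood urea nitrogen >23 mg/dL and uric acid >7.0 mg/dL at Level 1. The creatinine increase, eGFR decrease and hemoglobin decrease and increase rows are judged against baseline.

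SAP 4.6.3.2 counts multiples of the upper limit of normal (ULN) in the same way for the hepatic tests: "during the postbaseline period will be summarized for all participants with a postbaseline value".

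The SAP version history (Version 2, row for Section 4.6) records the step: "For laboratory analysis, removed shift analysis, Treatment emergent high/low and add elevated or low values meeting specified levels". The only reason given is an update to the PSAP.

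SAP Section 1 states "There are no changes to the analyses described in the protocol", and SAP 4.9, the section meant for such changes, states "There are no changes but additional details are provided to the analyses described in the protocol".

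**The concern.** There are two linked problems.

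The first is documentation. Protocol 9.3.1, repeated in SAP 4.1, lets the SAP change a non-principal method provided the change and its justification are described. A reader who goes to Section 4.9 for changes is told that there are none.

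The second is sensitivity. A participant who enters above a fixed level and stays there is an event in either arm, whatever the drug does. Such participants carry no information about new onset, yet they pull the risk difference toward zero and raise its variance. Protocol 5.2, criterion 20, makes this plausible for low multiples of ULN: it states that "study participants with non-alcoholic fatty liver disease are eligible for participation" and excludes ALT or AST only above 3x ULN. None of the listed eligibility criteria limits lipids, blood urea nitrogen or uric acid.

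At stake is the ability of the categorical laboratory tables to show a real difference in new abnormalities. The efficacy conclusions are not touched.

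**Working it through.** **Text comparison.**

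| Place | Outcome | Condition on baseline |
|---|---|---|
| Protocol 9.3.5 | Treatment-emergent abnormality (given as an example) | Yes, by its name |
| SAP 4.6.3.3 with Appendix 11 | Any postbaseline value meeting a level | Only creatinine, eGFR and hemoglobin change |
| SAP 4.6.3.2 | Any postbaseline value at or above a multiple of ULN | None |
| SAP 1 and 4.9 | Declared unchanged | – |

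The statistical method is not the conflict: SAP 4.6 keeps Fisher's exact test as the default and adds a risk difference with its interval. The outcome definition is. SAP 4.1 has a row for "laboratory values elevated or low, vital signs and body weight categorical measures" that defines a baseline period, from screening to the day of first dose, with scheduled and unscheduled values. Section 4.6.3.3 states no rule that uses it for the fixed rows.

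**Inputs for the illustration.**
- Arm size: 888 randomized 1:1 gives 444 per arm. The plan's own figure reproduces: 754/0.85 = 887.1, rounded up to 888, and 888 × 0.85/2 = 377.4.
- Two-sided alpha 0.05 (Protocol 9.3.1).
- Assumptions, not in the documents: baseline prevalence b; new onset 10% against 5% among participants normal at baseline; share s of baseline-abnormal participants abnormal again after baseline, equal in both arms; every randomized participant has a postbaseline value.

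The plan states no power for laboratory comparisons, so there is no such figure to reproduce.

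**Formulas.**
- Any-postbaseline rate in an arm: b·s + (1 − b)·p, where p is that arm's new-onset risk; n = 444 per arm.
- Risk difference under that rule: (1 − b)(p1 − p0).
- Treatment-emergent rule: rates p0 and p1 with n = 444(1 − b) per arm.
- SE = √{[r0(1 − r0) + r1(1 − r1)]/n}, with r0 and r1 the two arm rates; power = Φ(RD/SE − 1.96).

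**Worked case, b = 10%, s = 100%.**
- Any postbaseline: 0.10 + 0.90 × 0.05 = 0.145 and 0.10 + 0.90 × 0.10 = 0.190, so RD = 0.045. SE = √[(0.1240 + 0.1539)/444] = 0.0250. Power = Φ(1.80 − 1.96) = 0.44.
- Treatment-emergent: n = 399.6 and RD = 0.050. SE = √[(0.0475 + 0.0900)/399.6] = 0.0185. Power = Φ(2.70 − 1.96) = 0.77.

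**Results, s = 100%.**

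| Baseline prevalence | RD, any postbaseline (points) | Power, any postbaseline | RD, treatment-emergent (points) | Power, treatment-emergent |
|---|---|---|---|---|
| 0% | 5.0 | 0.81 | 5.0 | 0.81 |
| 1% | 4.95 | 0.76 | 5.0 | 0.81 |
| 10% | 4.5 | 0.44 | 5.0 | 0.77 |
| 30% | 3.5 | 0.19 | 5.0 | 0.66 |
| 50% | 2.5 | 0.11 | 5.0 | 0.52 |

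Full persistence is not essential. Any-postbaseline power at 10%, 30% and 50% prevalence is 0.47, 0.21 and 0.11 with s = 80%, and 0.52, 0.23 and 0.12 with s = 60%.

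**Which rows are exposed.**
- Mainly the Level 1 non-hepatic fixed cut-offs. Levels 2 and 3 (for example triglycerides >500 mg/dL or LDL >190 mg/dL) are likely to be rarer at baseline.
- Among the hepatic categories: ALT/AST ≥1x, ALP ≥2x, GGT ≥2x and the direct bilirubin categories. Criterion 20 excludes ALT or AST >3x, total bilirubin >2x (except Gilbert's) and ALP >2.5x ULN at screening. Few participants should therefore start in the ALT/AST ≥3x and above, total bilirubin, or ALP ≥3x categories, and there the two definitions nearly coincide.

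**The case against.** The best defence has five parts.

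- **The protocol commitment is light.** Treatment-emergent abnormality appears as an example in a sentence about choice of test, and 9.3.5 leaves further detail to the SAP. This stands: the SAP may change the outcome. The protocol still asks for the change to be described and justified, and Sections 1 and 4.9 deny it.
- **The change is recorded.** A reader who sees only Sections 1 and 4.9 might infer an undisclosed substitution. The documents do not support that, because the version history lists the removal openly. What is missing is a justification beyond a reference to the PSAP.
- **Other analyses use baseline.** Liver tests and lipids have a log-scale MMRM with baseline as covariate, other analytes have change-from-baseline summaries, and 4.6.3.2 adds treatment-emergent hepatic event queries and liver-injury screening plots. This stands, and it rules out saying that a drug effect would be hidden. Mean-change analyses can still miss an effect confined to a minority, and 4.6.3.3 leaves no categorical comparison that separates new from pre-existing abnormality for the fixed rows.
- **Randomization protects validity.** One might infer bias, or that a chance baseline imbalance raises the false-positive rate. Neither follows: baseline abnormality is balanced in expectation, and the unadjusted comparison keeps its nominal error rate. The loss is in sensitivity.
- **The PSAP and table specifications are separate documents.** A treatment-emergent analysis may exist at program level. That cannot be judged here, and it would not correct the statements in this SAP.

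**Conclusion.** The point holds in limited form. The current protocol and SAP define the categorical laboratory outcome differently, and SAP 1 and 4.9 say that nothing changed. For fixed cut-offs common before dosing, the SAP rule shrinks the risk difference by the factor (1 − b) and costs power: 0.44 against 0.77 at 10% baseline prevalence and 0.19 against 0.66 at 30%.

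These figures are an illustration. They rest on assumed new onset of 10% against 5%, full persistence that is equal in the two arms, and prevalences that the documents do not give. As prevalence approaches zero the difference disappears.

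A reader might go further and infer that the whole hepatic analysis is weakened, or that laboratory signals would be masked. The screening limits in criterion 20 and the retained baseline-adjusted analyses do not support either reading. The comparisons are safety assessments without multiplicity adjustment or a power target, so the consequence is a less sensitive set of tables and an incorrect statement of changes.

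**What to change.** 1. In SAP 4.6.3.3, add a treatment-emergent comparison (risk difference and 95% CI) beside the any-postbaseline table. For each fixed level, restrict numerator and denominator to participants with baseline and postbaseline values who do not already meet that level in the baseline period defined in SAP 4.1. The baseline-relative rows need no change.
2. Do the same in SAP 4.6.3.2 for ALT/AST ≥1x, ALP ≥2x, GGT ≥2x and the direct bilirubin categories. The higher multiples can stay as they are.
3. Correct the statements of no change in SAP 1 and 4.9, and list this change in 4.9 with its justification.

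The cost is SAP wording, one filter in the table programs and one extra set of tables. No new data are needed. The downside is smaller denominators that differ by analyte.
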